#### **4.2.3 Other efficacy variables**

For the analysis of the double-blind 52-week treatment period, other binary efficacy variables will be treated in the same way as the primary analysis of the primary efficacy variable (composite endpoint). That is, a subject will be considered a responder only if the response is achieved and if the subject is still on their randomized double-blind study treatment at the time

when the variable is evaluated. Analyses of other continuous efficacy variables will be based on LOCF. A sensitivity analyses will be performed on all other efficacy variables using observed case analysis as described for the primary endpoint in [Section 4.2.1](#).

For analysis of the Week 156/SFE-WD visit data, binary efficacy variables will be analyzed using the non-responder imputation (NRI) approach; that is, where the denominator is all subjects in the SFE-FAS for the given treatment group. A subject will be considered a responder only if the response criterion of the given variable is achieved. All other subjects will be counted as not responding e.g. subjects who have not achieved the given outcome and all subjects with missing data are set to non-response.

An observed case analysis of binary efficacy variables at Week 156/SFE-WD will be performed. The Observed Case analysis at Week 156, will consider a subject a responder only if the response is achieved. Non-response at Week 156 visit will be counted as non-responders. Early withdrawals or subjects with missing data will be considered missing in this analysis. The sensitivity analysis of the Observed Case analysis at Week 156/SFE-WD will consider a subject as a responder if response is achieved at Week 156/SFE-WD visit such that both subjects with a Week 156 visit (subjects who complete) and subjects with early withdrawal visits and efficacy results meeting the criteria of response, will be counted as a responder. Subjects with missing data will be considered missing in this analysis.

For continuous efficacy variables, the observed data at Week 156/SFE-WD visit will be analyzed. This will summarize efficacy data for completers and subjects with early withdrawal visits during SFE together. In addition, the efficacy data collected at Week 156 for completers only will be summarized.

#### 4.2.4 Safety variables

For analyses of AEs and concomitant medication usage, a complete date must be established in order to correctly identify the AE or medication as occurring during treatment or not. If time of study treatment and time of event or concomitant medication is available and non partial then it will also be used however if missing or partial, only the dates will be compared. For purposes of imputing missing components of partially-reported start and stop dates for AEs and for medication use, the algorithms listed below will be followed.

- Missing start day, but month and year present:

If the start of double-blind study medication occurred in the same month and year as the occurrence of the AE/concomitant medication, the start day of the event/concomitant medication will be assigned to the day of first administration of study medication during the double-blind period. Otherwise if informed consent was signed in the same month and year as the occurrence of the AE/concomitant medication, the start day of the event/concomitant medication will be assigned to the day of informed consent.

Otherwise if the following conditions are met:

- the year of the occurrence of the AE/concomitant medication is after the year of the end of the double-blind period or

- the year of the occurrence of the AE/concomitant medication is the same as the year of the end of the double-blind period and the month of the occurrence of the AE/concomitant medication is the after the month of the end of the double-blind period

then the following imputations will be done:

If the year of the occurrence of the AE/concomitant medication is the same as the start of the open-label period and the month of the AE/concomitant medication is the same as the month of the start of the open-label period then the start day of the event/concomitant medication will be assigned to the first day of the open-label period.

Otherwise if the year of the occurrence of the AE/concomitant medication is the same as the start of the SFE period and the month of the AE/concomitant medication is the same as the month of the start of the SFE period then the start day of the event/concomitant medication will be assigned to the first day of the SFE period.

Otherwise the start day will be set to the 1st day of the month.

- Missing start day and month, but year present:

If the start of double-blind study medication occurred in the same year as the occurrence of the AE/concomitant medication, the start day and month will be assigned to the date of first administration of double-blind study medication. Otherwise if informed consent was signed in the same year as the occurrence of the AE/concomitant medication, the start day and month will be assigned to the day and month of informed consent.

Otherwise if the year of the occurrence of the AE/concomitant medication is after the year of the end of the double-blind period and then the following imputations will be done:

If the year of the occurrence of the AE/concomitant medication is the same as the start of the open-label period then the start day and month of the event/concomitant medication will be assigned to the first day of the open-label period.

Otherwise if the year of the occurrence of the AE/concomitant medication is the same as the start of the SFE period then the start day of the event/concomitant medication will be assigned to the first day of the SFE period.

Otherwise the start day and month will be set to January 1st.

- Missing start day, month, and year:

The start date will be replaced by the date of first study drug administration of double-blind study medication or by the first day of January of the year of the end date, if the first administration date of double-blind study medication is after the end date.

- Missing end day, but month and year present:

The end day will be set to the last day of the month.

- Missing end day and month, but year present:

If the maximum of the subject's date of study termination or the date equivalent to 70 days after the subject's last administration of study medication is the same year as the occurrence of the AE/Concomitant medication, then the end day and month will be set to the maximum

of the date of study termination or the date equivalent to 70 days after last administration of study medication. Otherwise the end day will be set to December 31st of the given year.

- If the stop date is completely unknown, the stop date will not be imputed.

#### **4.2.5 Other considerations**

Descriptive summaries for all efficacy variables collected during the double-blind 52-week treatment period based on observed case data (including only subjects still on their randomized double-blind study treatment) will also be prepared.

### **4.3 Interim analyses and data monitoring**

An interim analysis is planned after the completion of the double-blind period of the last subject at Week 52. The timing of the analysis will be when the last subject completes Week 52 visit in accordance with the double-blind, OL-CZP or OL-OT schedule. At this time, all visit based data from the double-blind period up to and including Week 52 visit, all open-label visit based data up to Week 52 visit, all available Follow-up data for subjects already completing the study, all hospitalization/emergency room visit and health care provider consultation data, all study medication discontinuation and all prior and concomitant medication data including concomitant medical procedures, will be locked. Subjects still on the study awaiting Follow-up visit or in SFE, will continue to have AEs, laboratory, vital sign, PK and physical examination data collected per schedule until completion of the Follow-up or SFE period, at which point they will complete the study termination eCRF page. At the time of the interim analysis Week 52 DB lock, adverse event data entered to date will be cleaned but not locked. This will allow ongoing adverse event entry during the Follow-up and SFE periods. The treatment codes will be made available to the study reporting team and an interim study report will be written. All tables, listings and figures described in this SAP for analysis of the double-blind 52-week treatment period will be produced at the time of the Week 52 DB lock. The Investigators and subjects will remain blind to the assigned CZP dose regimen of the double-blind period.

After the last subject has completed the SFE period, the database will be fully locked, and a final study report will be written. For subjects in the SFE period, from the Week 52 visit onward, subjects will be treated with OL-CZP until Week 156/SFE-WD visit. During this time, only adverse events, concomitant medication related to adverse events, and study drug dispensation information will be collected. Efficacy assessments and study termination data will be collected at Week 156/SFE-WD as described in Table 5-6 of the study protocol. Therefore, at the final DB lock, the following tables and listings will be produced.

- Table 1.1.2: Disposition of Subjects Screened
- Table 1.2.1: Disposition and Discontinuation Reasons
- Table 1.2.2: Number of Subjects Completing each Visit
- Table 1.3: Disposition of Analysis Sets
- Table 1.4.1: Important Protocol Deviations During SFE
- Efficacy tables for analysis of efficacy data collected at Week 156/SFE-WD visit per Table 5-6 of the study protocol
- Table 7.1: Extent of Exposure

- Adverse Event Tables
- Laboratory Tables in order to include any data collected at the Follow-up visit post Week 52 interim database lock for subjects not entering SFE
- Listing 1.2: Subject Disposition
- Listing 1.3: Study Termination
- Listing 1.4: Visit Dates
- Listing 3.1: Important Protocol Deviations
- Listing 4.1: Subject Analysis Sets
- Efficacy listings for all efficacy data collected at Week 156/SFE-WD visit per Table 5-6 of the study protocol
- Adverse Event listings
- Laboratory listings in order to include any data collected at the Follow-up visit post Week 52 interim database lock for subjects not entering SFE.

Regular monitoring of safety data collected during the study will be performed as described in the Safety Signal Detection in the Ongoing Clinical Trials Charter for CZP.

A specific data monitoring-, steering-, or evaluation-committee is not planned for this study.

#### **4.4 Multicenter studies**

Due to the low number of subjects expected to be recruited per site, results will not be tabulated by individual sites. However important protocol deviations will be tabulated by region and the number of subjects randomized per region will also be presented. Listings will show the region and site for each subject. In addition, as subject randomization is stratified by region, efficacy analyses models will include region as a factor as described in [Section 8](#).

#### **4.5 Multiple comparisons/multiplicity**

The statistical analysis of the primary efficacy variable and selected secondary efficacy variables will account for multiplicity by using a fixed sequence testing procedure. Further details on how the hierarchical testing will be implemented is provided in [Section 8](#).

#### **4.6 Use of an efficacy subset of subjects**

The PPS will be used to evaluate subjects who have efficacy data during the double-blind treatment period and are reasonably compliant with the conditions of the study. This analysis set will provide additional information on the efficacy analysis and will describe findings in a subset of subjects who more closely follow the intentions of the study protocol.

The Randomized Set will be used to evaluate all subjects who were randomized to double-blind study medication. This analysis set will provide additional information on the efficacy analysis by describing findings in the full set of subjects who were randomized and will not exclude those who did not receive at least 1 dose of study medication or did not have a valid Baseline efficacy measurement for ASDAS.

Other than the planned sensitivity analyses based on the PPS and Randomized Set, no other efficacy subsets are defined for statistical analyses during the double-blind 52-week treatment period. The SFE-FAS is defined for analysis of efficacy data at the Week 156/SFE-WD visit.

#### 4.7 Active-control studies intended to show equivalence

Not applicable.

#### 4.8 Examination of subgroups

Subgroups for age (18 – < 45 years,  $\geq 45$  years), gender (male, female), race (white, other), symptom duration (<5,  $\geq 5$  years), tobacco use (never, current former), HLA-B27 genotype (positive, negative), region (North America, Europe, Asia), prior anti-TNF exposure (yes, no), Baseline SPARCC score (<5,  $\geq 5$  as observed in the 2nd reading session or in the 1st if the 2nd reading is not available), subjects with/without relevant changes to background medication, and MRI/CRP classification (MRI+/CRP+; MRI+/CRP-; MRI-/CRP+) will be utilized for summarizing the primary efficacy variable. Only summary statistics, estimates and confidence intervals will be presented and subjects with missing category will be excluded.

It is possible, that classification errors may occur within the randomization where a subject is found to have been randomized according to the wrong MRI/CRP strata when their MRI data and CRP results are re-examined post randomization. For this reason, the MRI/CRP classification, which will be used in all analyses and subgroup analyses will be one recalculated using the Screening MRI results and second Screening visits CRP results (3 to 5 days prior to Baseline). If the CRP result from the second screening visit is missing, available results from the first screening visit will be used.

Subjects will be categorized as MRI + if they have active (acute) inflammation on MRI highly suggestive of sacroiliitis associated with SpA as determined by the central readers. Otherwise they will be classed as MRI -.

Subjects will be categorized as CRP+ if their second Screening visit CRP result is  $>ULN$ . CRP values  $\leq ULN$  will be considered CRP-. If the CRP result from the second screening visit is missing, available results from the first screening visit will be used. In the unlikely event that a subject has an unavailable recorded CRP result pre Baseline, they will be considered CRP+ for analyses of efficacy but missing for other CRP summaries.

Based on these definitions, the analysis variable for MRI/CRP classification will have the following 3 levels:

- MRI+/CRP+
- MRI+/CRP-
- MRI-/CRP+

Any subjects found to be MRI-/CRP- will have their MRI and CRP data examined to see which of the category thresholds they were close to. The subject will still be included in the FAS analyses however they will be assigned into the respective positive category (MRI+/CRP+, MRI+/CRP- or MRI-/CRP+) that they were closest to and documented to have failed inclusion criterion #9. Hence, they will be excluded from per protocol analyses.

Symptom duration will be categorized into  $<5$  and  $\geq 5$  years for subgroup analyses and calculated as:

Start date of symptoms – date of first study medication administration

The start date of symptoms will be found using the medical history of the subject using the following rules (including imputation of partial dates as described in [Section 4.2.4](#)):

- Subjects with a medical history preferred term of ‘Back pain’ or ‘Inflammatory pain’ will use the earliest start date of these symptoms as the start date of symptoms.
- Otherwise, subjects with a preferred term of ‘Axial spondyloarthritis’ will use the earliest start date of disease as the start date of symptoms
- Otherwise, the subject’s medical history will be reviewed in the DEM meeting to determine if the subject has evidence of a start date of symptoms or primary disease.
- Otherwise, the median duration of subjects with a valid symptom duration within the same stratum regarding MRI/CRP classification, will be used as the symptom duration of the subject, unless the duration is  $<3$  months in which case 3 months and 1 day will be used.

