#### 2.1.2 Secondary objectives

The secondary objectives of the study are to assess efficacy, safety, and tolerability and to demonstrate the effect of CZP on:

- Health outcomes
- Disease activity
- SI joint inflammation
- Changes to concomitant and background medications

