### 8.1.2 Primary analysis of the primary efficacy variable

The primary analysis for of the primary efficacy variable will be based on logistic regression. The odds ratio of the ASDAS-MI responder rates at Week 52 will be estimated and tested between treatment groups using a logistic regression model with factors of treatment group, region, and MRI/CRP classification (MRI+/CRP+; MRI+/CRP-; MRI-/CRP+). The MRI/CRP classification used in all statistical analysis will be recalculated using source data as described in [Section 4.8](#) and the IXRS MRI/CRP categorization will not be used. If the logistic regression model is unable to converge, then the MRI/CRP classification variable may be dropped from the model to facilitate convergence. The study design is likely to result in some sites with a small number of enrolled subjects. The use of region as a factor in the model is intended to combine study centers in similar geographic regions. The geographic regions to be used will be as defined in the IXRS randomization system. In the unlikely event that a subject moves sites during the study which leads to a change in region, the region originally used at randomization will be used in the analysis.

Given the composite endpoint definition described in [Section 8.1](#), there will be no missing data for the primary endpoint, as subjects that discontinue double-blind study treatment prior to Week 52 or who do not have an ASDAS-MI response at Week 52 are considered non-responders to the double-blind study treatment.

Tables will present the responder rates for placebo and CZP 200mg, the respective effect estimates (adjusted odds ratio with reference to placebo), p-values, and 95% confidence intervals (CIs). The odds ratios and 95% CIs will also be presented graphically.

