### 8.1.3 Supportive and sensitivity analyses of the primary efficacy variable

As described in [Section 6.3](#) of the protocol, subjects who discontinue study treatment will not necessarily be withdrawn from the study. In an attempt to minimize missing data, efforts will be made to continue to collect safety and efficacy data on these subjects through study completion. In order to assess the impact of various missing data assumptions on the analysis, four sensitivity analyses of the primary efficacy variable will be performed as described in [Section 4.2.1](#). Further details of these analyses are provided in this section. The odds ratios  $\pm$  95% CI's for the primary analyses and sensitivity analyses will be presented on the same graph to allow visual comparison of the robustness of the results. In addition, a summary of the missing data pattern will be provided.

For Canada (and any other country where applicable or where requested by Regulatory Authorities), the primary efficacy variable measurement is the ASAS40 response at Week 12. Analysis of the ASAS40 response at Week 12 will be performed as described above for

ASDAS-MI response at Week 52 (including all sensitivity and subgroup analyses). Similar to the ASADAS-MI efficacy endpoint, the primary analysis of ASAS40 will be treated as a composite endpoint when it is analyzed. Specifically, subjects will need to: 1) achieve the relevant response (ASAS40); and 2) remain in the study and on their randomized double-blind study treatment through Week 12.

In addition to the above analyses, subgroup summaries using descriptive statistics, estimates and confidence intervals only for the primary efficacy variable by age, gender, race, symptom duration, tobacco use, HLA-B27 genotype, region, prior anti-TNF exposure, Baseline SPARCC score ( $<5$ ,  $\geq 5$ ), subjects with/without relevant changes to background medication, and MRI/CRP classification (MRI+/CRP+; MRI+/CRP-; MRI-/CRP+) will be performed.

The logistic regression analyses of the composite endpoint for ASDAS-MI responder rates at Week 52 (as described in [Section 8.1.2](#)) will also be repeated using the PPS and the Randomized Set. In addition, the primary analysis will be repeated where ASDAS-MI includes the criteria ASDAS reduction (improvement) of  $\geq 2.0$  relative to Baseline only.

### 8.1.3.1 Including observed data at Week 52

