### 8.1.3.2 Multiple imputation

Investigators will be given discretion to discontinue study treatment for subjects not responding in order to provide them with other treatments for the condition. Therefore, in many cases, missing efficacy data due to study treatment discontinuation should be dependent on the observed efficacy scores, but independent of unobserved data. This would be consistent with a missing at random (MAR) pattern of missingness. In order to investigate the efficacy results under the assumption of data being MAR, a multiple imputation method will be applied as follows:

1. The continuous ASDAS score at each visit will be calculated using the methods described in [Section 8.1.1](#) (including the application of LOCF if only one component is missing). Visits with more than one component missing will be set to missing. ASDAS data collected after the discontinuation of double-blind study treatment will be treated as missing in the original data set for this sensitivity analysis. Hence, all open-label period data is excluded from this analysis.
2. For subjects with a non-monotone (intermittent) missing pattern, MCMC will be used to impute their missing intermittent ASDAS scores including treatment arm, region, MRI/CRP

classification and ASDAS measurement from previous visit(s) as explanatory variables in the model. This will be done 100 times limiting the imputation to in range results.

After this step there will be 100 datasets containing all subjects however the only missing data will be a monotone missing data pattern. A variable called “\_imputation\_” will identify each of the 100 imputed datasets output.

3. The remaining missing data for all subjects with a monotone missing data pattern will be imputed using regression with treatment arm, region, MRI/CRP classification and ASDAS measurement from previous visit(s) as explanatory variables. This model will be run once for each of the imputed datasets limiting imputation to in range results.
4. The ASDAS change from Baseline to Week 52 will be calculated using the complete datasets (with no missing data) and categorized as: ASDAS-MI or not ASDAS-MI (as defined in [Section 8.1.1](#))

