#### **8.2.1.5 Relevant changes to background medication**

For purposes of this secondary efficacy variable, relevant changes to background medication will be defined as the following:

- The addition of a new DMARD or the change from one DMARD to another
- The addition of an NSAID or the change from one NSAID to another
- Increased dose of chronic oral corticosteroids
- Increased dose in chronic analgesic medications or the addition of a chronic analgesic medication

The variable to be measured is the number of subjects without relevant changes to background medications. Therefore, a subject who does not have any of the above relevant changes made to background medication during the study through Week 52 will be considered to have met this endpoint. Conversely, subjects who have one of the above relevant background medication changes or who do not complete double-blind study treatment to Week 52 will be considered as not having met this endpoint.

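### The primary endpoint is subgrouped by background-medication change through Week 52, a post-randomization variable that the SAP also analyses as a treatment outcome

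*SAP*

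**What the plan says.** Section 4.8 names "subjects with/without relevant changes to background medication" among the subgroups for the primary efficacy variable, and section 8.1.3 repeats it ("subjects with/without relevant changes to background medication, and MRI/CRP classification"). The other factors in the list, such as age, HLA-B27 genotype, prior anti-TNF exposure and Baseline SPARCC score, are fixed at or before baseline. On output, 4.8 says "Only summary statistics, estimates and confidence intervals will be presented". Section 8.1.2 gives the adjusted odds ratio as the effect estimate for this endpoint.

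The only derivation of the factor is in 8.2.1.5. It lists four kinds of medication event. A subject with none of them "made to background medication during the study through Week 52 will be considered to have met this endpoint". Subjects with such an event, or "who do not complete double-blind study treatment to Week 52 will be considered as not having met this endpoint".

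For the primary endpoint, 8.1.2 states that "subjects that discontinue double-blind study treatment prior to Week 52 or who do not have an ASDAS-MI response at Week 52 are considered non-responders".

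The SAP also treats the factor as something that treatment should change. Section 2.1.2 includes "Changes to concomitant and background medications" among the effects of CZP to be demonstrated, and 8.2.2.1 compares the arms on this variable with the logistic model used for the primary endpoint. Section 8.1.3.2 adds that "Investigators will be given discretion to discontinue study treatment for subjects not responding".

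Section 8.1.3 extends every subgroup analysis to ASAS40 at Week 12, the primary variable for Canada.

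**The concern.** A subgroup estimate is a treatment effect only if membership is settled before treatment can influence it. Here membership is decided during treatment. The subjects compared within each class are no longer the groups that randomization made comparable.

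Under 8.2.1.5 the factor and the endpoint also share a component. Not completing double-blind treatment keeps a subject out of the without-change class and also makes that subject a non-responder. The without-change class then contains completers only, and the with-change class collects every subject who is a non-responder because of discontinuation.

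The two resulting odds ratios would be printed beside true baseline subgroups with nothing to mark them as different. A gap between them could be taken as evidence that the effect of CZP depends on background medication, when it may only reflect who stayed on treatment and who changed medication in each arm.

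**Working it through.** **The plan's own figure.** Section 2.4 states 95% power for 40% vs 20%, 150 per arm, two-sided 0.05. With the pooled normal approximation, z = [0.20 − 1.96·√(2·0.3·0.7/150)] / √(0.4·0.6/150 + 0.2·0.8/150) = (0.2000 − 0.1037)/0.0516 = 1.86, so power is 0.969 (0.959 with continuity correction). The figure is sound and is not in dispute. The overall odds ratio is (0.4/0.6)/(0.2/0.8) = 2.67.

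**Inputs.** Response r is 40% (CZP) and 20% (placebo), from section 2.4. The SAP gives neither the proportion d not completing double-blind treatment nor the proportion q of completers with a relevant change, so both are assumed. Change is taken as unrelated to response within completers of an arm.

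**Formulas, applying 8.2.1.5 and 8.1.2.** Every responder is a completer, so:

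- Response without change = r(1−q)/[(1−d)(1−q)] = r/(1−d)
- Response with change = rq/[d + (1−d)q]
- Odds ratio = [pC/(1−pC)]/[pP/(1−pP)]

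**One case in full.** Take d = 15%/55% (CZP/placebo) and q = 20% in both arms.

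- Without: 0.40/0.85 = 47.1% vs 0.20/0.45 = 44.4%; odds ratio 0.889/0.800 = 1.11.
- With: 0.08/(0.15 + 0.17) = 25.0% vs 0.04/(0.55 + 0.09) = 6.25%; odds ratio 0.333/0.0667 = 5.00.

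**Range at 40% vs 20%.**

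| d, CZP/placebo | q, CZP/placebo | Without: rates, OR | With: rates, OR |
|---|---|---|---|
| 15%/55% | 20%/20% | 47.1% vs 44.4%, 1.11 | 25.0% vs 6.25%, 5.00 |
| 20%/40% | 20%/20% | 50.0% vs 33.3%, 2.00 | 22.2% vs 7.7%, 3.43 |
| 30%/30% | 10%/30% | 57.1% vs 28.6%, 3.33 | 10.8% vs 11.8%, 0.91 |
| 30%/30% | 20%/20% | 57.1% vs 28.6%, 3.33 | 18.2% vs 9.1%, 2.22 |

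The first two rows make the effect look larger with change, and the third makes it look larger without. In the fourth row nothing differs by arm. The risk ratio is then 2.0 in both classes, and the odds ratios differ only because the odds ratio depends on the underlying rate. If no completer changes medication (q = 0), the with-change class has 0% response in both arms and its odds ratio cannot be estimated.

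**Under no overall effect (20% vs 20%).** With d = 20%/50% and q = 20% in both arms:

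- Without: 0.20/0.80 = 25% vs 0.20/0.50 = 40%; odds ratio 0.50.
- With: 0.04/0.36 = 11.1% vs 0.04/0.60 = 6.7%; odds ratio 1.75.

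These are apparent effects in opposite directions where the overall effect is nil. With equal d and equal q, both odds ratios are 1.00.

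**ASAS40 at Week 12.** Under the Week 52 definition, a Week 12 responder who leaves double-blind treatment at Week 30 cannot be in the without-change class. The grouping draws on information from up to 52 − 12 = 40 weeks after the endpoint.

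**The case against.** **The derivation is not fixed.** Neither 4.8 nor 8.1.3 points to 8.2.1.5, and the non-completion rule there is written for the secondary endpoint. The subgroup could be built from the four medication events alone, with any missing category excluded as 4.8 provides. This stands. A reader might infer that the subgroup certainly absorbs all non-completers, but the SAP does not say so; that is only the likely reading. On the narrower reading the figures above do not apply, and the distortion depends on how change differs by arm among subjects with the same response status. The factor is still observed after randomization and still expected to respond to treatment.

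**Bias is not automatic.** A reader might also infer that the definition alone biases both estimates. It does not: equal completion and equal change rates preserve the null and the risk ratio. Distortion needs a difference between arms. The SAP's secondary objective and the discretion to discontinue non-responders make one foreseeable, without establishing it.

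**The magnitudes rest on assumed rates.** This is correct, and the range reverses direction, so no particular bias can be claimed.

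**The analysis is descriptive.** No subgroup test is planned and the subgroups lie outside the fixed sequence. That limits the consequence, but 4.8 still calls for estimates and confidence intervals.

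**Outputs already exist.** Sections 2.2.1.3 and 8.1.1 refer to double-blind outputs already produced, and under 4.3 treatment codes are released to the reporting team at the Week 52 lock. This weighs against adding new subgroups or composites now, and it affects the form of the fix.

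**Conclusion.** The concern holds with those limits. The primary endpoint is split by a post-randomization variable that the SAP itself analyses as an outcome of treatment. Under the only stated derivation, that variable also shares non-completion with the endpoint. Where completion or medication change differs by arm, the stratum odds ratios do not estimate treatment effects and cannot show whether the effect depends on background medication.

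Size and direction are undetermined. The span from 1.11/5.00 to 3.33/0.91 (without/with), against 2.67 overall, rests on the 8.2.1.5 derivation, the planned 40% and 20%, and the assumed rates in the table. The SAP does not support a claim of a known bias in a known direction. The primary test, alpha and power are untouched, so this is a reporting defect that should be corrected and does not threaten the main conclusion.

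**What to change.** Remove this factor from the subgroup lists in 4.8 and 8.1.3, for ASDAS-MI at Week 52 and for ASAS40 at Week 12. The extension-period subgroup list in 8.4 already omits it.

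If it is kept because outputs already exist:

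- present it apart from the baseline subgroups and label it as a post-randomization description;
- state which derivation is used;
- give response counts by arm, with no treatment-effect odds ratios or confidence intervals;
- show double-blind non-completers as a category of their own.

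The cost is a wording change in two sections and one row removed per subgroup display. If the displays have already been issued, the cost is one relabelled descriptive table with a sentence of explanation in the report. No sample-size, alpha or data-collection change follows.
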